### 15.3.3 Statistical design for correlative study A091105-ST1

See the note in [Section 15.2](#), which will apply to all analyses for this section A091105-ST1.

Statistics for Core #1: Archival FFPE and TMA studies: Associations among the possible predictors of response to sorafenib and CTNNB1 mutations will be examined using Fisher’s exact test, Kruskal-Wallis test, or Spearman’s correlation coefficient as appropriate. Variables considered include *CTNNB1* genotype, tumor size, tumor site, gender, age at initial diagnosis, and primary versus recurrent disease. Strata will be compared by using the log-rank test. Multivariate models will be constructed by introducing all variables aforementioned simultaneously into the model and then eliminating variables using the backward selection method. *P* values will be two-tailed and considered significant at alpha 0.05. Analyses will be conducted using SAS for Windows (release 9.3; SAS Institute, Cary, NC).

Statistics for Core #2: Microarray: A two-sided t-test will be used to identify differentially expressed genes on log transformed data and those with a twofold change. False discovery rate (FDR) will be assessed by permutation testing ( $n = 1000$ ) of the sample group labels. The selection approach is to first compute two *t*-tests and fold changes for each comparison between pre-treatment and day 8 versus the normal skin biopsy. Genes that have a nominal *p* value < 0.01 and fold > 2 for each comparison will be selected. To assess FDR,

permutation testing of the same selection will be performed 1000 times and the sample group labels switched around in each permutation. Java TreeView color maps will be generated. To unravel a treatment-specific gene expression signature, the analysis will identify over- and under-expressed genes in pre- treatment and day 8 biopsies as compared to all control samples (germlineDNA extracted from whole blood). Using Sigterms, sorafenib associated gene signature will search for Gene Ontology (GO) annotation terms, gene sets curated by the Molecular Signature Database (MSigDB, v2.5 and top enriched transcription factor sequence motifs. Enrichment will be assessed by one-sided Fisher's exact test with estimated FDR.

Statistics for Core #3 and 4: For each paired sample, differences in protein levels will be compared by paired t-test. This sample size of 75 patients will allow 93% power to detect 1 standardized difference. Quantitative changes in IHC score of VEGF, PDGFR and  $\beta$ -catenin cytoplasm/nuclear ratio will be correlated with disease status at 1 year by Fishers exact test.

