### 10.3 A091105-ST1 “Analysis of archival tissue, and pre-treatment and day 8 tumor biopsy and blood samples” (Optional)

#### 10.3.1 Objectives

- The mechanism of action of sorafenib in DT/DF remains unknown. All patients will undergo treatment tumor biopsies. Treatment induced changes will be quantified by histology, gene expression profiling, proteomic changes and selected interrogation of key pathways by Western blot and RT-PCR.
- To collect archival tissue, pre-treatment biopsies and blood and day 8 biopsies and blood specimens for basic science research.

Three recurrent mutations in beta-catenin gene have been documented and prognosticate risk of local recurrence after surgery. However, there is no study that has attempted to evaluate whether these mutations are predictive biomarkers of response to sorafenib. We will attempt to answer this question in this prospective study.

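### CTNNB1 mutations are to be assessed as predictive of sorafenib response with a model that has no treatment arm and no arm-by-genotype term, so a purely prognostic mutation could be reported as predictive

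*Combined protocol and SAP*

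**What the plan says.** Section 10.3.1 notes that "there is no study that has attempted to evaluate whether these mutations are predictive biomarkers of response to sorafenib" and commits the trial to the question: "We will attempt to answer this question in this prospective study". The same paragraph says: "Three recurrent mutations in beta-catenin gene have been documented and prognosticate risk of local recurrence after surgery". It therefore names both the predictive question and its main rival explanation, prognosis.

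The only statistical plan for this question is the Core #1 paragraph of Section 15.3.3. It begins with univariate work: "Associations among the possible predictors of response to sorafenib and CTNNB1 mutations will be examined using Fisher’s exact test", or by Kruskal-Wallis or Spearman methods. It adds a log-rank comparison of strata that it does not define. It lists the variables considered as CTNNB1 "genotype, tumor size, tumor site, gender, age at initial diagnosis, and primary versus recurrent disease", and then says: "Multivariate models will be constructed by introducing all variables aforementioned simultaneously into the model and then eliminating variables using the backward selection method". Significance is two-tailed at 0.05. Randomised arm and an arm-by-genotype term are not listed. The outcome, the type of model and the population (both arms or sorafenib only) are not stated.

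Sections 5.4.2 and 10.3.4 require ST1 to be offered to every patient. Section 10.3.2 takes genotype from the archival block of consenting patients, and Section 6.3.1 makes that block mandatory for everyone. Genotype will therefore be available in both arms.

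**The concern.** A marker is predictive if the effect of treatment differs by marker status. A marker is prognostic if it shifts outcome whatever the treatment. Telling them apart needs a treatment contrast within each genotype, that is, an arm-by-genotype term fitted to both arms.

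The listed model has no such term under either reading of the population. With arms pooled, the genotype coefficient averages over treatments. In sorafenib patients alone, it mixes prognosis and prediction with nothing to separate them. Backward selection only removes terms, so it cannot restore one that was never entered.

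At stake is the interpretation of a biomarker result. The trial has a randomised placebo arm, which is the one feature that lets the question be asked properly, and the stated model does not use it.

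**Working it through.** The documents give no sample size, prevalence, effect size or power for the CTNNB1 analysis, so there is no stated figure to reproduce. The calculation below illustrates how often a purely prognostic mutation would appear significant.

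**Inputs from Section 15.1.1.** Median PFS 6 months on placebo and 15 on sorafenib (hazard ratio 0.40), 75 patients allocated 2:1 (50 and 25), 4 patients per month, at least 12 months of follow-up.

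**Inputs assumed here.** PFS outcome; binary genotype with 30% or 50% prevalence; prognostic hazard ratio of 1.5 or 2, equal in both arms; 75 or 38 genotyped patients (38 being about half).

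**Check of the borrowed inputs.** Accrual lasts A = 75/4 = 18.75 months, with F = 12. With monthly hazard λ = ln 2/median, the event probability is 1 − [exp(−λF) − exp(−λ(A+F))]/(λA).
- Expected events are 22.4 on placebo and 30.8 on sorafenib, 53.2 in all.
- Scaled to 52 events (21.9 and 30.1), the standard error of the log hazard ratio is √(1/21.9 + 1/30.1) = 0.281.
- At one-sided 0.0255 the critical hazard ratio is 0.578 and power is 90.5%. The plan states 0.5776 and 90%, so the inputs reproduce the main design.

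**Simulation.** There were 2,000 trials per setting, with exponential PFS. The 6- and 15-month medians apply to the reference genotype. Each Cox model was tested at two-sided 0.05. The other five covariates and the selection step were left out. Monte Carlo standard error is at most √(0.25/2000) = 1.1 percentage points.

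| Patients | Prevalence | Prognostic HR | Genotype, pooled, no arm | Genotype, sorafenib only | Genotype adjusted for arm | Arm-by-genotype |
|---|---|---|---|---|---|---|
| 75 | 30% | 1.0 | 4.7% | 4.9% | 5.2% | 5.9% |
| 75 | 50% | 1.0 | 4.4% | 5.0% | 4.8% | 6.0% |
| 75 | 30% | 1.5 | 27.6% | 22.5% | 32.0% | 5.4% |
| 75 | 50% | 1.5 | 26.7% | 20.9% | 30.8% | 5.3% |
| 75 | 30% | 2.0 | 60.4% | 47.3% | 69.4% | 5.9% |
| 75 | 50% | 2.0 | 65.7% | 52.9% | 74.8% | 5.1% |
| 38 | 30% | 1.5 | 16.3% | 12.7% | 18.9% | 6.4% |
| 38 | 50% | 1.5 | 16.0% | 11.7% | 19.5% | 6.1% |
| 38 | 30% | 2.0 | 35.8% | 27.6% | 41.8% | 6.0% |
| 38 | 50% | 2.0 | 39.6% | 28.0% | 45.9% | 6.4% |

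No mutation in this table is predictive, so a significant genotype term read as prediction is an error. Adding arm as a main effect does not help: the genotype term is then flagged slightly more often. Only the interaction column stays near its nominal level.

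**Power of the interaction test** (75 patients, 50% prevalence, no effect of genotype on placebo). Simulated power is about 22%, 39% and 53% for true ratios of hazard ratios of 2, 2.5 and 3. By formula, splitting each arm's events equally by genotype gives a standard error of √(2/11.2 + 2/15.4) = 0.555, so 80% power needs a ratio of exp(2.80 × 0.555) ≈ 4.7. With half the events the standard error is 0.555 × √2 = 0.785, and the ratio needed rises to exp(2.80 × 0.785) ≈ 9.0.

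**The case against.** The strongest reply is that this is an optional, exploratory correlative. Section 10.3.4 describes the ST1 laboratory work as exploratory, the correlative objectives in Section 2.3 do not list CTNNB1 prediction, and no efficacy decision rests on it. That stands, and it limits the weight of the point. It does not remove the mismatch: Section 10.3.1 still states a predictive aim, and Section 15.3.3 attaches a 0.05 significance rule.

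It can also be said that the variable list is worded as open-ended. But the model sentence is tied to the variables already named, and no other section adds arm. Where the authors want arm and a treatment interaction in a model, as in the mixed model of Section 15.3.2, they list them. The Section 15.2 note that governs ST1 only excludes or censors data on crossover treatment after the November 2017 unblinding.

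Four stronger inferences are tempting, and the documents do not support them.
- **A prognostic mutation would be reported as predictive.** It could be. The chance depends on the size of a prognostic effect on the chosen outcome. The documents record prognosis only for recurrence after surgery, not for PFS or response in this population.
- **The rates describe the planned analysis.** Section 15.3.3 names no outcome or population, so PFS in all 75 patients is an assumption.
- **A standard power formula gives the size.** Φ(ln HR × √(52 × 0.25) − 1.96) yields 31% at a hazard ratio of 1.5 and 71% at 2. It ignores the attenuation from omitting arm and is nearer the arm-adjusted column. It also depends on 50% prevalence, for which the documents give no source. Section 10.3.3 puts sporadic disease at about 85% and says sporadic desmoids carry these mutations. If 85% were the mutated share, 0.85 × 0.15 = 0.1275 replaces 0.25 and the same formula gives about 18% and 43%.
- **Fewer ST1 participants would lower every figure.** The rate of false genotype findings falls, but the interaction test's error rate stays near 6% and the detectable ratio rises.

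**Conclusion.** The point holds as a mismatch between aim and method. The plan asks a predictive question, identifies the same mutations as prognostic in another setting, and specifies a model that cannot separate the two under either reading of its population.

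Under the assumptions above, with 75 genotyped patients, a mutation that is not predictive at all is flagged in about 27-28% (hazard ratio 1.5) or 60-66% (hazard ratio 2) of trials with arms pooled, and 21-23% or 47-53% in sorafenib patients alone. With 38 patients the pooled rates are about 16% and 36-40%. An arm-by-genotype test stays near 5-7% throughout. These rates are illustrative, because prevalence, prognostic effect, outcome and number genotyped are all assumed. The structural conclusion does not depend on them. The primary efficacy analysis is unaffected.

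**What to change.** In Section 15.3.3:
- State the outcome, the type of model, the population and what the log-rank strata are. Include genotyped ST1 patients from both arms.
- Force arm, genotype and arm-by-genotype into the model, outside backward selection. Use one interaction term per non-reference genotype level, or prespecify a binary grouping. With three recurrent mutations and wild type as a fourth level, arm plus interactions adds four parameters (1 + 3).
- Report the treatment hazard ratio within each genotype and the interaction estimate with its confidence interval, labelled hypothesis-generating. Call genotype main effects prognostic.
- If the interaction cannot be estimated, for example because placebo cells are sparse for a response outcome, describe the result as associational and drop the predictive wording in Section 10.3.1.

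If PFS is chosen, crossover at progression comes after the event, and crossover from the November 2017 unblinding is already covered by the Section 15.2 note.

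The cost is a text change and a few model terms, with no new tissue or assay. The real downside is precision. Placebo has only 25 patients before optional consent, power is about 39% for a ratio of hazard ratios of 2.5 even with all 75 genotyped, and a ratio of about 4.7 is needed for 80%, more with fewer participants. The confidence interval will be wide, and a non-significant interaction would not show that the mutations are not predictive.

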We will also be evaluating diffusion-weighted MR imaging (DW-MRI) in a subset of patients having extra-abdominal disease. DW-MRI is a non-invasive technique that derives its image contrast from differences in the motion of water molecules between tissues. The degree of water diffusion in biologic tissue is inversely correlated to tissue cellularity and the integrity of cell membranes. The motion of water molecules is more restricted in tissues with high cellular density associated with numerous intact cell membranes (e.g., tumor tissue). Quantitative analysis of DW-MRI is achieved by calculation of the apparent diffusion coefficient (ADC). The ADC is calculated for each pixel of the image and is displayed as a parametric map.

RECIST 1.1: Twenty four of 26 patients were evaluable for response. CT or MRI was obtained at a median interval of 4 months. Responses by RECIST 1.1 were: 0/24 complete responses, 6/24 partial responses (25%), 17/24 (70%) with stable disease and 1 patient with progressive disease. Seven patients experienced minor response (defined as 10–29% decrease). Bi-dimensional WHO size measurements were highly correlated ( $R^2=0.92$ ) with RECIST (not shown). RECIST PR was achieved at a median of 10 months and a minor response (i.e. reduction > 10% by RECIST) was noted at a median of 4 months of starting therapy. PR and SD were mostly seen in extra-abdominal tumors ( $p=0.03$ , t-test) and there was no difference between those who received sorafenib as first-line or second-line ( $p = 0.9$ , t-test).

**Survival:** The 26 patients were followed for a median of 50 months (3–209 months) from initial diagnosis. Median follow-up from the start of sorafenib was 12 months (1-46+). Median time to progression was not reached. Five patients progressed despite sorafenib, defined as increasing tumor size (2), symptoms (1) or drug intolerance (2). Twenty-five of 26 patients are alive with disease.

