**Decision Rule:** We will randomize a total of 75 patients (25-placebo, 50-sorafenib) and observe patients until we have reached 52 PFS events for the efficacy analysis. In the event the median PFS in the control group is larger than expected and long-term follow-up becomes a concern, we will perform the final efficacy analysis after 52 events are observed or after all evaluable patients have been followed for at least 3 years, whichever occurs earlier. If the 1-sided p-value associated with the Log-Rank test is  $< 0.0255$  (corresponding to an observed HR of 0.5776), we will consider sorafenib as having shown promising activity in this population and may recommend it for further testing.

**Inefficacy/Futility Analysis:** We will evaluate the observed PFS of the arms when 45% of the PFS events required for the final efficacy analysis (i.e., 24) have been observed.

We will terminate the study for futility if the p-value associated with the test statistic from a Log-Rank is at least 0.5025 (corresponding to an observed HR of 1.0027). Otherwise, we will continue to complete full enrollment.

Although the primary endpoint will be evaluated using the first 75 evaluable patients, final efficacy results will further report results (e.g., publication, presentation) using all patients evaluable for determining PFS and so that patient enrolled beyond these 75 may contribute to these estimates.

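### Section 15.3.3 lets backward elimination remove CTNNB1 genotype, so its adjusted effect goes unreported unless it survives selection, and is then likely to be exaggerated

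*Combined protocol and SAP*

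**What the plan says.** Section 10.3.1 lists two objectives for the optional substudy A091105-ST1: treatment-induced tissue changes and specimen collection. It then turns to the beta-catenin gene: "Three recurrent mutations in beta-catenin gene have been documented". It notes that "there is no study that has attempted to evaluate whether these mutations are predictive biomarkers of response to sorafenib" and says the trial will attempt to answer that question.

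The analysis is in Section 15.3.3 under Core #1. The variables are CTNNB1 "genotype, tumor size, tumor site, gender, age at initial diagnosis, and primary versus recurrent disease". Associations are tested by Fisher's exact test, Kruskal-Wallis or Spearman correlation. In addition, "Strata will be compared by using the log-rank test". The multivariable step is then: "Multivariate models will be constructed by introducing all variables aforementioned simultaneously into the model and then eliminating variables using the backward selection method". Significance is judged two-sided at the 0.05 level.

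The section does not:
- force genotype into the model;
- give a separate criterion for staying in the model;
- name the outcome or the type of model;
- ask for the full-model genotype effect with a confidence interval;
- correct the p-values of retained variables for the selection.

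Core #2, in the same section, does get permutation testing and false-discovery control.

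**The concern.** Backward elimination treats the marker of interest like any other covariate. If genotype is removed, the plan commits to no adjusted estimate of its effect. If it stays, it does so because its estimate passed a significance threshold. In a small sample that means an estimate above the truth, with a p-value that ignores the selection. The remaining variables pass through the same filter, so the final model may list predictors that are chance findings.

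At stake is the reportable adjusted answer to the CTNNB1 question, and a possible published list of independent predictors. No primary or secondary endpoint depends on it.

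**Working it through.** **1. Sample size.** The plan gives no sample size, power or event count for this model. The one related figure is in Section 15.1.1: "We will randomize a total of 75 patients (25-placebo, 50-sorafenib". This reproduces: 75 × 2/3 = 50. At the maximum accrual of 83 (Section 15.1.2), 83 × 2/3 = 55. The ST1 consent rate is not stated, so 25 is used below only as an assumed low case.

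**2. Information per variable.** Section 1.10 reports 6 of 24 partial responses, or 25%, in the retrospective series. If the outcome is response:
- n = 50: 50 × 0.25 = 12.5 responders; 12.5/6 = 2.1 per variable. If genotype takes 3 parameters (three mutations plus an assumed wild-type level), there are 3 + 5 = 8 parameters and 12.5/8 = 1.6 per parameter.
- n = 25: 6.25/6 = 1.0 per variable.
- n = 83, all patients: 20.75/6 = 3.5 per variable.

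If the outcome is PFS with a 15-month median, n = 50 gives about 31 events (assuming censoring uniform from 12 to 31 months), or 31/8 = 3.9 per parameter.

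**3. False predictors.** Six independent tests at 0.05 give 1 − 0.95^6 = 26.5% with no selection at all. Simulated backward elimination with no true predictor gave at least one survivor in:
- likelihood-ratio tests, four-level genotype (assumed mix 25/35/25/15%): about 28-34% at n = 50 and 39-45% at n = 25;
- Wald tests in simpler logistic models: 19-25% at n = 50.

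**4. Exaggeration when genotype is retained.** Take n = 50, a binary genotype with 30% prevalence, 25% response overall and a true OR of 3. The response rates are then 0.404 in 15 carriers and 0.184 in 35 non-carriers.
- SE(log OR) = √[1/(15 × 0.404 × 0.596) + 1/(35 × 0.184 × 0.816)] = √(0.277 + 0.190) = 0.683
- Smallest OR that reaches p < 0.05, approximately: exp(1.96 × 0.683) = 3.8

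A retained OR must exceed about 3.8 when the truth is 3. In 2,000 simulated studies the median retained OR was 6.7 for a true 3 and 8.0 for a true 5.

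**5. How much loss is due to selection?** Logistic model, n = 50, prevalence 30%:

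| True OR | Dropped by backward elimination | Missed by one prespecified test (1 − power) |
|---|---|---|
| 3 | 62% | 1 − 0.383 = 62% |
| 5 | 38% | 1 − 0.663 = 34% |

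Cox model with a genotype hazard ratio of 2, compared with a fixed model of genotype, site and size:

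| n | Dropped by backward elimination | Non-significant in fixed model |
|---|---|---|
| 50 | 56-62% | 58-61% |
| 25 | 66-68% | 70-72% |

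With no genotype effect, genotype was retained in 8-10% at n = 50 under selection, against 7-9% significant in the fixed model. Selection therefore adds little to the chance of missing the effect, and at n = 50 little to its false retention. It changes what is reported.

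**The case against.** The strongest reply is that the CTNNB1 question does not rest on the selected model. The same section plans Fisher, Kruskal-Wallis or Spearman tests and a log-rank comparison, none of which involves selection. Genotype is tested whatever the model drops. This stands, and it limits the point to the adjusted estimate and its interval. The listed tests yield p-values and do not commit the plan to an effect size with a CI.

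Second, a reader might infer from the high drop rates that backward elimination causes a real effect to be missed. Step 5 shows otherwise: a fixed model misses it about as often.

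Third, a reader might take 50 sorafenib patients as a ceiling, or 25 as a realistic floor. The documents support neither. Maximum accrual gives about 55, Section 15.3.3 does not restrict the model to the sorafenib arm, and placebo patients who cross over at progression might be included. In the other direction, ST1 is optional with no stated consent rate, although the archival block itself is required of every patient.

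Fourth, CTNNB1 is not the only purpose of ST1. Section 10.3.1 gives mechanism of action and specimen collection as objectives, and the hypothesis in Section 10.3.3 concerns paired biopsies. That lowers the weight of the point without removing it, since the section still says the question will be attempted.

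**Conclusion.** The concern holds in a limited form. The only multivariable model for the CTNNB1 question can discard genotype, and the plan then commits to no adjusted effect or CI. When genotype is kept, its effect is likely to be overstated (median OR 6.7 for a true 3 at n = 50). With no true predictor, some variable survives in roughly 28-34% of studies at n = 50 and 39-45% at n = 25 under likelihood-ratio elimination. That compares with 26.5% for six plain tests, and the figure is lower under Wald elimination with simpler coding.

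These figures rest on assumed genotype frequencies, effect sizes, outcome model, stay level (0.05) and sample size, because the documents give none of these for this model. It would go too far to say that the substudy could end with no genotype result, or that a fixed model would find more true effects. This is a cheap improvement to an exploratory substudy.

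**What to change.** In Section 15.3.3, Core #1, replace the backward-selection sentence with:

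> CTNNB1 genotype is kept in the model whatever its p-value, adjusted for intra-abdominal disease (yes/no) and tumor size, and its estimate and 95% CI are reported. The other variables are described one at a time, as exploratory, without selection.

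Intra-abdominal disease is already a stratification factor (Section 5.6), so it needs no new data. The same edit should name the outcome, the model and the genotype coding. A permutation p-value is optional.

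The cost is wording only. The other variables are no longer screened jointly, and the genotype interval will be wide: in the step 4 scenario, 3 × exp(±1.96 × 0.683) is about 0.8 to 11.5. Power is unchanged, at about 34-38% for an OR of 3 at n = 50 over genotype prevalences of 20-50%.

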### 2.3 Correlative Companion Study Objectives

- 2.3.1 To evaluate changes in MRI T2 to predict (or correlate) with a biological effect such as tumor growth (by RECIST v1.1), and pain palliation.
- 2.3.2 The mechanism of action of sorafenib in DT/DF remains unknown. In patients consenting to undergo the paired tumor biopsies (A091105-ST1), treatment induced changes will be quantified by histology, gene expression profiling, proteomic changes and selected interrogation of key pathways by Western blot and RT-PCR.
- 2.3.3 To collect archival tissue, baseline (tumor, blood) and day 8 (tumor, blood) specimens for basic science research (A091105-ST1).
- 2.3.4 To assess patient-reported adverse events and quality of life (QOL) as measured by the PRO-CTCAE and the single-item overall LASA (A091105-HO1).
- 2.3.5 To assess pain palliation measured by the “worst pain” item of the Brief Pain Inventory Short Form (A091105-HO1).

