## 5.6 Stratification

Patients will be stratified at randomization by:

- 1) intra-abdominal disease: yes vs no

2) baseline level of pain (BPI “Worst Pain” Item: 0-<3; 3 – <7 vs 7 – 10). See [Appendix V](#).

We will be using a 2:1 randomization scheme to improve accrual to the study given that it has an observation arm and to also reduce biopsies performed for patients who have been enrolled to the placebo group. The randomization algorithm used by the Alliance Statistics & Data Center uses dynamic allocation procedure which balances the marginal distributions of the stratification factors between treatment regimens.

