### 10.3.4 A091105-ST1 Biopsies

#### Pre- and day 8 (+ 7 days) post-randomization biopsy guidelines

A091105-ST1 must be offered to all patients enrolled on A091105 (although patients may opt to not participate). Patients who consent to A091105-ST1 will undergo 2 biopsies (pre-treatment and day 8 post-randomization).

The following exploratory studies will be performed and analyzed in the laboratory of [name], correlative chair. Bio-informatics analysis will be provided by MSKCC Bio-informatics core lab. Blood, pre-treatment and day 8 matched tumor biopsies are required elements of this study for patients. Patients will undergo 2 biopsies (procuring 5 cores for each biopsy) by interventional radiology under image guided CT or U/S. Core biopsies will be evaluated for the following studies: 1) one core will be formalin fixed for pathological studies and TMA construction, 2) 1 - 2 cores will be used for gene array expression profiling to determine a sorafenib signature of response, whole exome sequencing, microRNA array and epigenetics 3) one core will be used for a constrained evaluation of phospho-proteomic changes utilizing a Zaptosens reverse protein array of selected pathways identified from genetic studies.

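### The Core #3 and 4 protein analysis specifies only a before/after paired t-test and no sorafenib-versus-placebo contrast, so as written it cannot separate a drug effect from biopsy or time effects

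*Combined protocol and SAP*

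**What the plan says.** Section 15.3.3, under Core #3 and 4, states: "For each paired sample, differences in protein levels will be compared by paired t-test". The power statement follows at once: "This sample size of 75 patients will allow 93% power to detect 1 standardized difference". The only other analysis there relates changes in IHC scores to disease status at 1 year, which is not an arm comparison. The laboratory description of Core #3 and #4 in Section 10.3.4 sets out the same contrast, pre-treatment against day 8. The note in Section 15.2, which Section 15.3.3 applies to all ST1 analyses, deals only with crossover treatment after the November 2017 unblinding.

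The purpose is given in Section 2.3.2: "treatment induced changes will be quantified by histology, gene expression profiling, proteomic changes". Section 10.3.1 repeats it, and Section 10.3.3 hypothesizes pathways that sorafenib modulates.

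ST1 is offered to patients in both arms, and those who consent have a biopsy before treatment and another at day 8 (Section 10.3.4). Section 5.6 gives as one reason for 2:1 allocation "to also reduce biopsies performed for patients who have been enrolled to the placebo group". The number of placebo biopsies is therefore reduced, not brought to zero. Section 15.1.1 splits the 75 patients into 50 on sorafenib and 25 on placebo.

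**The concern.** A paired test of day 8 against pre-treatment shows that something changed between the two biopsies. It does not show that sorafenib changed it. Any systematic effect of the first five-core biopsy, or of elapsed time, moves the mean difference in the same way as a drug effect would.

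The trial is randomized and double-blind, so it has the right control: placebo patients with the same two biopsies on the same schedule. The written protein analysis gives those pairs no role as a control. At stake is whether a pathway that moves in both arms could be taken for one that sorafenib modulates, and whether biopsies taken from placebo patients inform the question they could best answer.

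**Working it through.** **Inputs.** From Section 15.3.3: a paired t-test, 75 patients, 1 standardized difference, 93% power. No alpha is given for Core #3 and 4. I assume two-sided 0.05 from the Core #1 text ("values will be two-tailed and considered significant at alpha 0.05") and try 0.01, which appears only in the Core #2 gene-selection rule ("value < 0.01 and fold > 2 for each comparison will be selected"), as a variant. From Section 15.1.1: 50 sorafenib, 25 placebo. The ST1 consent rate and the size of any non-drug shift are not in the documents, so both are shown as ranges. All effects are in units of the SD of the within-patient change.

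**Step 1. The plan's own power figure.** For a paired t-test, power comes from the noncentral t distribution with n − 1 degrees of freedom and noncentrality d√n. With n = 75 and d = 1, the noncentrality is √75 = 8.66 and the two-sided 0.05 critical value is 1.99. Power is above 99.9%, so 93% is not reproduced. A paired test reaches 93% with about 14 pairs at 0.05, or 20 pairs at 0.01. The closest match that uses all 75 patients is a two-sample comparison of 50 v 25 at two-sided 0.01: 92.1% by noncentral t, 93.4% by normal approximation. The plan states neither that test nor that alpha for these cores.

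**Step 2. Rejection rate with no drug effect.** Let the same non-drug shift δ occur in both arms. The paired test then has noncentrality δ√n. For example, δ = 0.3 gives 0.3 × √30 = 1.64 with 30 pairs and 0.3 × √75 = 2.60 with 75.

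| Assumed shift δ | 30 pairs | 75 pairs |
|---|---|---|
| 0.1 SD | 8% | 14% |
| 0.2 SD | 19% | 40% |
| 0.3 SD | 36% | 73% |
| 0.5 SD | 75% | 99% |

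Restricting the paired test to the 50 sorafenib pairs does not solve the problem: 28%, 55% and 93% at 0.2, 0.3 and 0.5 SD. A between-arm test of the change stays at 5% throughout, because the common shift cancels.

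**Step 3. Dilution, only if arms are pooled.** With a 1 SD effect on sorafenib and none on placebo, the pooled mean change is (50 × 1 + 25 × 0)/75 = 0.67 SD.

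**Step 4. Power of a between-arm test.** For a two-sample t-test of the change, the noncentrality is d√(n₁n₂/(n₁ + n₂)), with d = 1 and two-sided 0.05.

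| Pairs, sorafenib v placebo | Noncentrality | Power |
|---|---|---|
| 50 v 25 | 4.08 | 98% |
| 30 v 15 | 3.16 | 87% |
| 20 v 10 | 2.58 | 70% |
| 15 v 8 | 2.28 | 59% |
| 10 v 5 | 1.83 | 39% |

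**The case against.** **The plan is silent on arm; it does not exclude an arm comparison.** This stands. Section 15.3.3 does not say whether pairs are pooled, split by arm or limited to sorafenib. A reader might infer that biopsy or time changes will be reported as treatment-induced. The documents contain no such reporting rule; that reading comes only from the wording of the objective. What can be said is that the one written test cannot separate the two. Pooling is likewise only suggested by the use of all 75 patients, so the 0.67 SD figure is conditional.

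**The 93% may come from a between-arm calculation.** The near match to 50 v 25 at 0.01 is suggestive but proves nothing, since that alpha is not stated for these cores. If it is the source, the intended test is not the one written. Either way, test and power disagree.

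**The shift may be small or absent.** This is fair: at 0.1 SD the excess over 5% is modest. It is tempting to cite the link between trauma and desmoids in Section 1.1 as evidence of a shift, but that section calls the link weak, and it concerns tumor development, not protein levels at day 8. The request in Section 6.3.2 to sample different tumor areas when possible does not help the concern either. It may lessen local wound carry-over, and unless site choice is related to time it adds variance, not a mean shift.

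**Dilution does not by itself favor a between-arm test.** Correct. With 30 pooled pairs (20 and 10), a 1 SD effect on sorafenib only gives a mean of 0.67 and an SD of about √(1 + 2/9) = 1.11. Treating the mixture as normal, power is about 89%, against 70% for the between-arm test. The case rests on confounding alone.

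**These are exploratory laboratory studies.** True, and it limits the importance of the point. It does not make a before/after test answer a question about the drug.

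**Conclusion.** The point holds in a limited form. The only protein-level test written for Core #3 and 4 is within-patient, the stated aim is treatment-induced change, and a randomized control with the same paired samples has no stated role. Followed as written, the analysis confounds drug effect with biopsy and time effects. How much this matters depends on a shift that the documents do not give: over assumed values of 0.1 to 0.5 SD, rejection with no drug effect ranges from 8% to 75% with 30 pairs and from 14% to 99% with 75. Those rates assume the same shift in both arms and two-sided 0.05.

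Separately, and without any assumed shift, the 93% power does not match a paired t-test on 75 pairs at that alpha.

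The documents do not show that an arm comparison is ruled out, that arms will be pooled, or that non-drug changes will be reported as drug effects.

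**What to change.** In Section 15.3.3, Core #3 and 4:

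- Make the inferential test a between-arm ANCOVA of the day-8 protein level adjusted for the pre-treatment level, or a two-sample t-test of the change.
- Keep paired tests within each arm as descriptive.
- State the alpha, and replace the 93% with power for the between-arm test at the number of consenting pairs expected in each arm.

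The cost is wording only, with no new samples or visits. The downside is lower power, which becomes serious if uptake is low. Participation is optional, depends on biopsy being safe and feasible, and has no stated rate. The step 4 powers are for the two-sample test of change at an unadjusted 0.05, with no allowance for testing many proteins. If only 15 v 8 or 10 v 5 pairs are expected, the plan should say that the between-arm result will be an estimate with a wide interval.
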